6.8 Confounding Variables

Patients entering weight loss programs which promote exercise, surgeries which reduce body fat by significant degree, getting a physical trainer during course of study.

6.9 Bias

The study sample size is reasonably small introducing the possibility of selection bias. To minimize this risk, we are employing simple, straightforward inclusion and exclusion criteria and minimizing the total number of criteria to make our study population as similar to a general HF population as possible. Other sources of bias, including misclassification bias will be minimized by the direct electronic dataflow from randomization to data capture from the Pattern Health App, and direct data streams from Abbott medical to the Pattern Health app. Recall bias will be minimized because questions regarding symptoms will be asked to reflect the current symptoms, not a recollection of prior symptoms. Observer bias will be minimized by the objective nature of the physical activity measurement used in the primary endpoint.

7 TABLES, FIGURES, AND LISTINGS

Table	Title	Population
1. Disposition		
Table 1	Subject Enrollment and Status Summary	All enrolled
2. Demographics and Past Medical History		
Table 2.1	Demographics and Baseline Characteristics	ITT
Table 2.2	Demographics and Baseline Characteristics	AT
Table 2.3	Medical History at Baseline	ITT
Table 2.4	Medical History at Baseline	AT
3. Primary Endpoint Analysis		
Table 3.1.1	Primary Endpoint P1: Trajectory of the median Abbott ICD and CRT-D device measured daily PA obtained over baseline and treatment period	ITT
Table 3.1.2	Primary Endpoint P1: Descriptive statistics of the median Abbott ICD and CRT-D device measured daily PA obtained over baseline and treatment period	ITT
Table 3.2.1	Primary Endpoint P1: Trajectory of the median Abbott ICD and CRT-D device measured daily PA obtained over baseline and treatment period	AT
Table 3.2.2	Primary Endpoint P1: Descriptive statistics of the median Abbott ICD and CRT-D device measured daily PA obtained over baseline and treatment period	AT
Table 3.3	P1: Sensitivity Analysis for Imputed Data	ITT
Table 3.4*	P1: Sensitivity Analysis for Transformed Data	ITT
4. Secondary Endpoint Analysis		
Table 4.1.1	Secondary Endpoint S1: Change from baseline KCCQ HF symptom severity score to the last week of study	ITT
Table 4.1.2	Secondary Endpoint S1: Change from baseline KCCQ HF symptom severity score to the last week of study	AT
List 4.2	Secondary Endpoint S2: Adverse Events: heart failure hospitalization, fracture, myocardial infarction, serious adverse arrhythmia, and ICD therapy	ITT and AT
Table 4.3.1	Secondary Endpoint S3: Association between daily PA measured by the Abbott ICD or CRT-D device and in KCCQ HF symptoms severity score measured between baseline and end of follow up	ITT
Table 4.3.2	Secondary Endpoint S3: Association between daily PA measured by the Abbott ICD or CRT-D device and in KCCQ HF symptoms severity score measured between baseline and end of follow up	AT

*These tables will be intentionally blank if sensitivity analysis unnecessary.

Figure	Title	Population
Figure 3.1.1	Predicted Trajectories of the Mean Abbott ICD and CRT-D Device Measured Daily PA by Random Group	ITT
Figure 3.1.2	Trend of the Median Abbott ICD and CRT-D Device Measured Daily PA by Random Group	ITT
Figure 3.2.1	Predicted Trajectories of the Mean Abbott ICD and CRT-D Device Measured Daily PA by Random Group	AT
Figure 3.2.2	Trend of the Median Abbott ICD and CRT-D Device Measured Daily PA by Random Group	AT

Patient-level data listings will be produced to accompany the above tables and figures

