### 10.1.1 PATIENT REPORTED DATA AND DEVICE DATA

Patient reported data collected via the Pattern Health Patient App include weight, questionnaire responses, blood pressure and blood sugar, review of current medications, recent hospitalization and the presence of symptoms (shortness of breath or chest pain).

Devices used in this study will be integrated with the Pattern Health App and the data collected will be passively uploaded to the Duke EMR.

Device data for this study include:

- Abbott Medical ICD or CRT-D implantable device: heart rate, daily physical activity, physical activity intensity, and heart failure severity

All AEs will be gathered electronically through the Pattern health smartphone application. The study coordinator will request addition information through the App on an individual basis. In the event that a subject fails to respond to requests for data through the App, a follow-up telephone call will be placed by a study coordinator. All AEs will be recorded in the eCRF.

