#### 14.2.3 CLASSIFICATION OF AN ADVERSE EVENT

The following categories will be used to classify AE in the protocol.

- **Mild** – Events that will require minimal or no treatment intervention and does not interfere with the participant's daily activities.
- **Moderate** – Events that could result in a low-level inconvenience or concern with the prescribed therapeutic measures. A moderate event may cause interference with normal functioning.
- **Severe** – Events that can interrupt a study participant's typical daily activity and would require systemic drug therapy or another intervention/treatment. Severe events can pose as potentially life-threatening or incapacitating. Note, the terms severe and serious are not necessarily equal.

Relatedness: AEs that result from the presence, application, or performance of the remotely administered exercise regimen will be considered system related. AEs that are not temporally related, that affect organ systems or body-sites that are not affected by the exercise regimen, or that can be attributed to another cause will be considered unrelated.

Adverse Event relationships to the study intervention will be classified as either related to study participation or not related to study participation. Expected and unexpected AEs will be clearly delineated from one another. Expected AEs include worsening HF symptoms, orthopedic injury (including fracture, sprain, or tear of bone or soft tissue), myocardial infarction, serious arrhythmia, and ICD therapy. All other AEs will be considered unexpected.

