#### 14.2.4 ADVERSE EVENT REPORTING

Timely, accurate, and complete reporting and analysis of safety information for clinical studies are crucial for the protection of subjects. Reporting and analysis of safety data are mandated by regulatory authorities worldwide. AE CRF's will be collected for all AEs that are potentially study-related and all serious AEs regardless of their relationship to the study. For AEs that require immediate reporting, initial reporting may be done by phone, fax, email or on the CRF completing as much information as possible. The AE CRF must be completed as soon as possible. For any changes in status of a previously reported adverse event (i.e. change in actions taken, change in outcome, change in relatedness), an update to the original AE must be completed. All reported AEs must be followed until the AE has been resolved, is unresolved with no further actions planned, the subject dies or exits the study, or until study closure, whichever occurs first. In the event that a subject is exited from the study prior to study closure, all efforts should be made to continue following the subject until all unresolved system related AEs, as classified by the investigator, are resolved or they are unresolved with no further actions planned. At the time of study exit, all collected AEs with an outcome of "Unresolved, further actions or treatment planned" must be reviewed and an update to the original AE must be reported. At a minimum, if there are no changes to the description, relatedness, test and procedures or actions taken, the outcome must be updated to reflect "Unresolved at time of study closure."

All AEs will be reported to the sponsor and the IRB within 10 working days of the event.

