## 15 RISK BENEFIT AND CONFIDENTIALITY

## 15.1 RISK/BENEFIT ASSESSMENT

Study subjects randomized to the intervention study arm will perform more PA than normal for the 12 weeks of study participation. During this time, they may be subject to increased risks of muscle or joint strain, fracture, fall, or soft tissue swelling or pain. Additionally, study subjects may have a higher risk of heart failure hospitalization, myocardial infarction, serious adverse arrhythmia, and ICD therapy. There are no expected long-term risks. Risks will be minimized by designing an exercise regimen that provides small incremental increases in physical activity and further increases will be guided by feedback provided by subjects through the Pattern Health application.

Participation in the research study may have potential benefit. Prior retrospective studies suggest that increased PA is associated with improved 1-5 year survival and reduced risk of hospitalization in patients who meet study inclusion criteria. Further work suggests that increased PA is also associated with reduced frequency and severity of depressive symptoms.

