3.2 Secondary Objectives

- 3.2.1 Secondary Objective #1 Compare the effect of remote cardiac rehabilitation on baseline and 12 week Kansas City Cardiomyopathy Questionnaire (KCCQ) HF symptom severity scores versus usual management.
- *Outcome Measure:* Change in Kansas City Cardiomyopathy Questionnaire (KCCQ) HF symptom severity scores from the baseline to the 12 week
- 3.2.2 Secondary Objective #2 Report Adverse Events of the remote cardiac rehabilitation during the intervention period
 - *Outcome Measure:* Adverse Events: heart failure hospitalization, fracture, myocardial infarction, serious adverse arrhythmia, and ICD therapy
- 3.2.3 Secondary Objective #3 Association between daily PA measured by the Abbott ICD or CRT-D device and in KCCQ HF symptoms severity score measured between baseline and end of follow up.
 - *Outcome Measure:* Change in daily PA measured by the Abbott ICD or CRT-D device between baseline and week 12 of treatment period and change in KCCQ HF symptoms severity score measured between baseline and end of follow up

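### Sprains, strains, tears and falls are named and recorded as harms of the exercise, but fracture is the only injury in the one safety output the SAP specifies

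*SAP*

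**What the plan says.** **Harms named.** Protocol 15.1 says of patients in the exercise arm that "they may be subject to increased risks of muscle or joint strain, fracture, fall, or soft tissue swelling or pain". Protocol 14.2.3 puts on its list of expected adverse events "orthopedic injury (including fracture, sprain, or tear of bone or soft tissue").

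**Capture.** Protocol 10.1.1 states: "All AEs will be recorded in the eCRF". Protocol 14.2.4 sets a narrower rule for the dedicated form: "AE CRF's will be collected for all AEs that are potentially study-related and all serious AEs regardless of their relationship to the study".

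**Exemption.** Protocol 9.2.3 removes certain common disease-related events from reporting. Pain in muscles or joints is among them. Sprain, strain, tear and fall are not.

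**Planned output.** SAP 3.2.2 gives the objective as "Report Adverse Events of the remote cardiac rehabilitation during the intervention period" and then defines the outcome as five event types. SAP 6.4 (S2) repeats the five. List 4.2 in SAP section 7 carries them in its title: "Adverse Events: heart failure hospitalization, fracture, myocardial infarction, serious adverse arrhythmia, and ICD therapy". It is the only safety item in that section.

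**Broader wording.** Under S2, SAP 6.4 and Protocol 11.8.2 both promise an adverse-event listing for the study population, and that sentence sets no five-event limit of its own. Protocol 3.2 says adverse events will be reported between treatment groups, again without limiting them to five.

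**The concern.** Musculoskeletal injury is a foreseeable harm of exercise started remotely, without in-person instruction and without cardiopulmonary exercise testing (Protocol 1.4). The protocol anticipates it and arranges to record it. The results section then has a defined place only for fractures.

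Aim 3 (Protocol 9.1) says the trial will determine whether the exercise arm carries excess risk. Protocol 9.1 also says the results will be used to design a pivotal trial and to support a label expansion. There is no DSMB (Protocol 10.3, 12.5), so no such committee would tabulate the remaining injuries by arm. A programmer who works from the List 4.2 title would leave recorded sprains, tears and falls out of the safety results, and the intervention would look safer than the trial's own data show.

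**Working it through.** The plan states no figure to reproduce. The check is a cross-reading, followed by a simple illustration of size.

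**1. Each named harm traced to an output**

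| Term | Where named | Exempt under 9.2.3? | In List 4.2 title? |
|---|---|---|---|
| Fracture | 14.2.3, 15.1 | No | Yes |
| Sprain | 14.2.3 | No | No |
| Tear (bone or soft tissue) | 14.2.3 | No | No |
| Strain (muscle or joint) | 15.1 | Not listed; some could be coded as muscle or joint pain | No |
| Fall | 15.1 only | No | No |
| Soft-tissue swelling | 15.1 | Not listed | No |
| Soft-tissue pain | 15.1 | Possibly, as muscle or joint pain | No |

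One of the seven terms is in the title.

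**2. Other outputs that might carry the rest**

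No other table, listing or figure in SAP section 7 has adverse-event content. The patient-level listings promised at the end of that section accompany the named tables and figures, none of which is an adverse-event table. A tear or fall that leads to admission is a serious event under Protocol 14.2.2 and gets an AE CRF whatever its cause, but it too has no specified output unless it also involves one of the five events.

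**3. Size, on assumed rates**

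Let p be the proportion of rehabilitation patients with a non-fracture injury in 12 weeks. The documents give no value, so p = 5% to 20% is an assumption. Let n be the number of rehabilitation patients.

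- Expected number = n × p
- Chance of at least one = 1 − (1 − p)^n, with patients independent

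The documents give two totals. SAP 4.1 describes 13 patients, so about 6 or 7 per arm at 1:1. The protocol plans 50, so 25 per arm.

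| n | p | Expected | Chance of at least one |
|---|---|---|---|
| 6 | 5% | 6 × 0.05 = 0.30 | 1 − 0.95^6 = 26.5% |
| 7 | 5% | 7 × 0.05 = 0.35 | 1 − 0.95^7 = 30.2% |
| 6 | 20% | 6 × 0.20 = 1.2 | 1 − 0.80^6 = 73.8% |
| 7 | 20% | 7 × 0.20 = 1.4 | 1 − 0.80^7 = 79.0% |
| 25 | 5% | 25 × 0.05 = 1.25 | 1 − 0.95^25 = 72.3% |
| 25 | 20% | 25 × 0.20 = 5.0 | 1 − 0.80^25 = 99.6% |

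The SAP is the document that contains List 4.2, so its 13 patients are the more relevant base.

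**The case against.** **The five events are a legitimate prespecified choice.** They are the events of special interest in Protocol 9.2.3 and the content of Aim 3, and the synopsis, Protocol 11.8.2 and SAP 3.2.2, 6.4 and 7 all use them. A pilot may limit its safety endpoint in this way. That stands, and nothing here asks for a different S2 endpoint. It does not explain why other recorded injuries should have no defined output.

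**The listing sentence may already cover all adverse events.** Read alone, the sentence in SAP 6.4 and Protocol 11.8.2 could mean every recorded event, and Protocol 3.2 supports that reading. It sits under a five-event S2 definition, though, and the List 4.2 title restates the limit. The documents are therefore ambiguous, and two programmers could produce different safety reports. A reader might infer that List 4.2 is certain to show no such injuries; that assumes the narrow reading.

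**Injuries are reported elsewhere.** A reader might infer that these events are collected and never reported at all. The documents do not support that. Protocol 14.2.4 sends every adverse event to the sponsor and IRB within 10 working days, and Protocol 14.2.5 sends serious ones to the sponsor and NESTcc at once. These are notifications of single cases, however, and not a comparison of arms.

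**Capture is not unconditional.** Under Protocol 14.2.4 a non-serious injury gets an AE CRF only if it is potentially study-related, although Protocol 10.1.1 has all adverse events entered in the eCRF. Falls are named only as a risk in 15.1 and are absent from the expected events in 14.2.3. Some strains and soft-tissue pain could be absorbed by the 9.2.3 exemption. All of this stands and narrows the point, but sprains and tears remain squarely within it.

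**Conclusion.** The point holds as a gap in the specified outputs, together with an inconsistency over the scope of the adverse-event listing. Non-fracture injuries and falls are named, are to be recorded and are not expressly exempted, yet no SAP output clearly includes them. If List 4.2 is built to its title, the safety results will understate injury whenever such an event occurs.

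The size depends on the assumed 5% to 20% rate and on which enrolment figure applies. At the SAP's 13 patients, 0.3 to 1.4 non-fracture injuries are expected in the rehabilitation arm, with a 26.5% to 79.0% chance of at least one. At the protocol's 50, 1.25 to 5 are expected, with a 72.3% to 99.6% chance. A reader might infer that several injuries would be left out; at the SAP's sample size the documents do not support that, and there may be none. The reporting gap itself does not depend on these rates. This is a cheap correction that should be made, and it does not threaten the primary analysis.

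**What to change.** Keep the five events as the S2 endpoint. In SAP 6.4 and section 7, add one listing of all recorded adverse events, with counts by randomised arm, that flags orthopedic injury (fracture, sprain, strain, tear) and falls. State in SAP 6.4 how this listing relates to List 4.2, so that the listing sentence there and in Protocol 11.8.2, the commitment in Protocol 3.2 and the List 4.2 title agree.

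The cost is a few lines of SAP wording and one more listing from data already recorded. No endpoint, sample size, visit or clinical rule changes. The downside is that the safety report may look slightly less favourable.
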